8.3.1.4. Exposure to Study Medication and Compliance

Exposure

The actual duration of exposure in days will be calculated from the first study drug in MT-1186-A02 as follows

Exposure duration (days)=Date of last study drug – date of first study drug in MT-1186-A02 + 1

If the date of first study drug dose or the date of the last study drug dose cannot be determined, then the duration calculation will not be completed. Interruptions and compliance will not be considered for the duration of exposure.

Page 23 of 61

Confidential

Mitsubishi Tanabe Pharma America, Inc.

The total exposure in person years will be calculated as the sum of duration of exposure to study treatment over all patients in days divided by 365.25.

Treatment Compliance

Treatment compliance will be calculated for each subject using the following:

Treatment compliance(%)

 $Exposure \ duration - count \ of \ study \ medication \ days \ missed + \\ = \frac{count \ of \ additional \ study \ medication}{Exposure \ duration}$

 $\times 100\%$

The #count of study medication missed and additional study medication are collected by CRF visit.

Treatment compliance will be calculated using the formula above and reported to 1dp.

Date switched to PEG/RIG administration

If the date of switched to PEG/RIG administration is partial, then it will be imputed as follows:

- If the switched day is missing, the first day of the month will be used.
- If the switched day and month are missing, then the first day of the first month (January) will be used.

If the imputation date is earlier than date of the first study drug, the imputation date will be same as date of the first study drug.

8.3.2. Efficacy Measures

8.3.2.1. Time to 12-point decrease in ALSFRS-R or death

The primary end point in this study is the time from the randomization date in Study MT-1186-A02 to the first occurrence of at least 12-points decrease in ALSFRS-R or death, whichever happens first.

ALSFRS-R is a questionnaire used to measure the impact of ALS that is evaluated by the Investigator. The scale measures the subjects' physical function across 12 activities of daily living. The date of the evaluation along with the results will be recorded on the eCRF with respect to "4 Handwriting" and "5 eating motion," the results for the dominant hand (the hand used in daily life at the time of screening) will be recorded.

- ALSFRS-R total score for each visit will be derived from the sum of 12 items². For the item 5 "Eating disorder," either the item (a) or (b) will be selected corresponding to subjects with or without gastrostomy respectively. The maximum total score is 4 x 12=48.
- ALSFRS-R domains Score. The following subdomain will be calculated for each visit as well as the change from baseline to week 48.
 - O Bulbar function = total of items 1 to 3
 - O Limb function = total of items 4 to 9
 - o Fine motor function = total of items 4 to 6
 - O Gross motor function = total of items 7 to 9
 - o Respiratory function = total of items 10 to 12

The time to event variable will be calculated as follows:

Time to event=Event Date or Last Observed Date – Randomization Date + 1

- The time to the first occurrence of at least 12-point decrease in total ALSFRS-R score will be calculated from randomization date in MT-1186-A02 until last total ALSFRS-R score measurement available during MT-1186-A04. If the first occurrence of at least a 12-point decrease at any visit time point is observed, then the time variable will be calculated as the difference between the date that ALSFRS-R score was observed for which the above decreased occurred and the randomization date in MT-1186-A02.
- In case of death, the time variable will be calculated as the difference between death

² Refer to Appendix I of the protocol.

Mitsubishi Tanabe Pharma America, Inc.

date and the randomization date in MT-1186-A02.

• In case the subject did not experience either of the above events, the time variable will be calculated as the difference between date of the last observed date (Censored date) and the randomization date in MT-1186-A02.

In case the event of at least 12-point decrease in total ALSFRS-R score or death was observed, a censor variable will be created with value 0 and 1 otherwise.

8.3.2.2. Combined Assessment of Function and Survival (CAFS) score CAFS Scoring:

CAFS analysis ranks clinical outcomes on the basis of survival time and change in the ALSFRS-R score from baseline in Study MT-1186-A02 to all post baseline visits from MT-1186-A02 until the end of Study MT-1186-A04.

To calculate a patient's CAFS score, each patient is compared individually to all other patients in the study. The summary score for each patient is the sum of the comparisons (1, 0, 1) against all other patients (Figure 2). For each pairwise comparison of patients, the patient who fares better earns a point, and the one who fares worse loses a point. In the case of a tie, no points are added or subtracted. If both participants die, the one surviving longer fared better; if only one survives then that patient fared better; and if both participants survive, the one with the smaller decline in ALSFRS-R from baseline to week 48 fared better. If a participant discontinues early or ALSFRS-R data at week 48 are missing, the participant will be treated as alive at week 48 and the ALSFRS-R at week 48 will be imputed missing using multiple imputation under missing at random (MAR).

CAFS Ranking:

Next, patients' summary scores are ranked (

Mitsubishi Tanabe Pharma America, Inc.

Figure 3).

In general, the ranking has the following characteristics:

- (1) The first patient who dies will have the lowest score and is ranked the lowest;
- (2) the last to die is ranked above all others who die;
- (3) Among survivors, the patient with the greatest decline in ALSFRS-R is ranked just above the last patient who died;
- (4) The surviving patients with the least decline in ALSFRS-R is ranked highest;

[figure not shown]
The average rank score is then calculated for each treatment group. A higher mean rank score indicates that participants in that treatment group, on average, fared better.

Figure 2:

Mitsubishi Tanabe Pharma America, Inc.

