APPENDIX 2 ALS FUNCTIONAL RATING SCALE- REVISED (ALSFRS-R) (EXAMPLE)

1 Speech	6 Dressing and hygiene
4: Normal speech processes	4: Normal function
3: Detectable speech disturbance	3: Independent and complete self-care with effort or decreased efficiency
2: Intelligible with repeating	2: Intermittent assistance or substitute methods
1: Speech combined with nonvocal communication	1: Needs attendant for self-care
0: Loss of useful speech	0: Total dependence
2 Salivation	7 Turning in bed and adjusting bed clothes
4: Normal	4: Normal
3: Slight but definite excess of saliva in mouth; may have nighttime drooling	3: Somewhat slow and clumsy, but no help needed
2: Moderately excessive saliva; may have minimal drooling	2: Can turn alone or adjust sheets, but with great difficulty
1: Marked excess of saliva with some drooling	1: Can initiate, but not turn or adjust sheets alone
0: Marked drooling; requires constant tissue or handkerchief	0: Helpless
3 Swallowing	8 Walking
4: Normal eating habits	4: Normal
3: Early eating problems — occasional choking	3: Early ambulation difficulties
2: Dietary consistency changes	2: Walks with assistance
1: Needs supplemental tube feeding	1: Nonambulatory functional movement
0: NPO (exclusively parenteral or enteral feeding)	0: No purposeful leg movement
4 Handwriting	9 Climbing stairs
4: Normal	4: Normal
3: Slow or sloppy: all words are legible	3: Slow
2: Not all words are legible	2: Mild unsteadiness or fatigue
1: Able to grip pen but unable to write	1: Needs assistance
0: Unable to grip pen	0: Cannot do
5a Cutting food and handling utensils (subjects without gastrostomy)?	10 Dyspnea
4: Normal	4: None
3: Somewhat slow and clumsy, but no help needed	3: Occurs when walking
2: Can cut most foods, although clumsy and slow; some help needed	2: Occurs with 1 or more of the following: eating, bathing, dressing (ADL)
1: Food must be cut by someone, but can still feed slowly	1: Occurs at rest, difficulty breathing when either sitting or lying
0: Needs to be fed	0: Significant difficulty, considering using mechanical respiratory support
5b Cutting food and handling utensils	11 Orthopnea

Protocol MT-1186-A04

(alternate scale for subjects with gastrostomy)?	
4: Normal	4: None
3: Clumsy but able to perform all manipulations independently	3: Some difficulty sleeping at night due to shortness of breath, does not routinely use more than 2 pillows

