8.2. Data Handling Convention for Missing Data

In general efficacy data will not be imputed unless otherwise noted. For safety summaries, only observed data will be used. Unless otherwise specified, missing safety data will not be imputed. For each analysis variable, how to handle missing data are described in section 8.3 respectively.

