8.3.2.3. King's ALS Clinical Stage Derived from ALSFRS-R Score and Death Event

The King's ALS Clinical Staging System describes functional progression of ALS in terms of magnitude of disease involvement of different CNS regions (bulbar, upper limb, lower limb, need for gastrostomy and need for tracheostomy); according to its developers, the system was designed to inform patient-care decision making, resource allocation, research classifications, and clinical trial design¹¹. Stages 1, 2, and 3 refer to the number of CNS regions (bulbar, upper limb, lower limb) involved at assessment, as described in *Table 4* below. Stage 4A is defined solely by impairment of swallowing sufficient to require gastrostomy, and Stage 4B is defined solely by respiratory involvement sufficient to require ventilatory support. Functional involvement of three CNS regions is not a prerequisite to Stage 4A or 4B.

While the King's ALS Clinical Staging System was designed initially for use as an assessment tool to be used in clinic, Balendra and colleagues 12 developed a method for estimating King's ALS Clinical Stages based on responses to ALSFRS-R items Q1 (speech), Q2 (salivation), Q3 (swallowing), Q4 (handwriting), Q5A/Q5B (self-feeding), Q8 (walking), Q10 (dyspnea), and Q12 (respiratory insufficiency) 12. The algorithm for mapping from responses to these items to King's Stage is also described in *Table 4*.

Table 4: King's ALS Clinical Staging System

King's Stage	Definition	Item Mapping
1	Functional involvement of 1 CNS region	Bulbar involvement Score ≤3 on Q1, Q2, or Q3
2	Functional involvement of 2 CNS regions	Upper limb involvement Score ≤3 on Q4 or Q5A
3	Functional involvement of 3 CNS regions	Lower limb involvement Score ≤3 on Q8
4A	Need for gastrostomy	If Q5B is answered, rather than Q5A
4B	Need for non-invasive ventilation	Score of 0 on Q10 or score ≤3 on Q12
_5	Death	

CNS: Central nervous system regions are bulbar, upper limb, and lower limb

Mitsubishi Tanabe Pharma America, Inc.

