9.2.2.1.2. ALSFRS-R score - Changes from Baseline

The changes from baseline to (CHG) to all post-baseline visits throughout the periods of both MT-1186-A02 and MT-1186-A04 in ALSFRS-R will be included in a Mixed Model for Repeated Measures (MMRM) using SAS PROC MIXED. The model includes response data from all post-baseline visits with no imputation for missing data. The ALSFRS-R at baseline (BASE), randomization strata of ALSFRS-R rate of decline (DR) score during the screening period (2 levels strata of -1,-2 or -3,-4), Geographical Region (GR) (3 levels strata of Europe, America or Asia Pacific), Treatment Group (TRTP), Visit (AVISIT) and Treatment-by-Visit interaction will be included as fixed factors in the model. An unstructured covariance structure will be assumed, and the denominator degrees of freedom will be computed using the Kenward-Roger method. In case the model will not converge with the unstructured covariance structure, the heterogeneous compound symmetry (CSH) and the heterogeneous Toeplitz structure (TOEPH) will be used instead (in that order). The least-squares mean (LSMEANS) estimates for the mean change from baseline to Week 4 (A02), Week 8 (A02), Week 12 (A02), Week 24 (A02), Week 36 (A02), Week 48 (A02 and A04 Day1), Week 60 (A04 Week 12), Week 72 (A04 Week 24), Week 84 (A04 Week 36) and Week 96 (A04 Week 48), as well as the difference of the estimates between oral edaravone 105 mg daily versus oral edaravone 105 mg on/off regimen will be displayed with their corresponding standard errors, p-values, and 95% confidence interval. The same analysis will be conducted for each domain of ALSFRS-R. The SAS code planned for the primary analysis is outlined below.

9.2.2.1.3. Time to death, tracheostomy, or permanent assisted mechanical ventilation:

The secondary endpoint of time to death, tracheostomy, or permanent assisted mechanical ventilation (TIMETO2) will be analyzed similarly as the primary endpoint analysis using the stratified log rank (section 9.2.1.1).

[figure not shown]
Mitsubishi Tanabe Pharma America, Inc.

9.2.2.1.3.1. Supportive analysis for time to death, tracheostomy, or permanent assisted mechanical ventilation

- 1) Repeat the supportive analysis for the primary endpoint using Cox Proportional Hazard Model.

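### SAP 8.3.2.1 states the ALSFRS-R item 5a/5b selection rule in reverse of Protocol Appendix 2; probably a drafting slip, but it is the written scoring rule behind the primary endpoint

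*SAP*

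**What the plan says.** SAP 8.3.2.1 defines the score behind the primary event: "ALSFRS-R total score for each visit will be derived from the sum of 12 items", with a maximum of 48. Item 5 exists in two versions, and the SAP chooses between them as follows: "either the item (a) or (b) will be selected corresponding to subjects with or without gastrostomy respectively". The same section defines five domain scores. Two of them contain item 5: "Limb function = total of items 4 to 9", and fine motor function, which sums items 4 to 6.

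Protocol Appendix 2, which reproduces the instrument, heads the first version "5a Cutting food and handling utensils (subjects without gastrostomy" and describes version 5b as the "alternate scale for subjects with gastrostomy". Table 4 in SAP 8.3.2.3 assigns King's Stage 4A, need for gastrostomy, on the condition "If Q5B is answered, rather than Q5A".

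On missing values, SAP 8.2 states: "In general efficacy data will not be imputed unless otherwise noted". For the ALSFRS-R MMRM, SAP 9.2.2.1.2 states: "The model includes response data from all post-baseline visits with no imputation for missing data". CAFS is an exception: SAP 8.3.2.2 and 9.2.2.1.1 prescribe multiple imputation under missing at random.

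SAP section 2 makes the SAP's analysis details prevail over the protocol's statistical description. SAP section 11 lists one change from the protocol, the definition of the full analysis set.

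**The concern.** The order in the SAP sentence is fixed by its last word, and it is the opposite of the order on the instrument. Nothing suggests that this was intended: section 11 is silent, and the SAP's own staging table follows the instrument. But because section 2 lets the SAP govern, a programmer or a quality-control reviewer who turns to the SAP for the derivation finds the inverted rule.

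The sentence feeds the total used for the 12-point primary event, the baseline ALSFRS-R covariate in the Cox model, CAFS and the ALSFRS-R MMRM. It also feeds the limb and fine-motor scores, since 9.2.2.1.2 repeats the MMRM for each domain. An error here would reach most of the efficacy analyses.

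**Working it through.** No planned figure needs to be reproduced. The check sets the three statements side by side and then counts what the literal rule could do.

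| Source | Item 5a | Item 5b |
|---|---|---|
| SAP 8.3.2.1, item 5 sentence | with gastrostomy | without gastrostomy |
| Protocol Appendix 2 | without gastrostomy | with gastrostomy |
| SAP 8.3.2.3, Table 4 | not the sign of gastrostomy | answered means Stage 4A, need for gastrostomy |

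Two of the three agree, and the SAP scoring sentence is the odd one out. It is intact prose, so broken table extraction does not explain it.

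**Inputs.** Twelve items scored 0 to 4 (Appendix 2); total 12 × 4 = 48, which matches the stated maximum and does not depend on the order of 5a and 5b. Domain definitions (SAP 8.3.2.1): bulbar items 1–3, limb 4–9, fine motor 4–6, gross motor 7–9, respiratory 10–12. Item 5 therefore enters the total and 2 of the 5 domains.

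**Case 1: only the applicable version is filled in.** This is what the wording of Table 4 implies. The literal rule then selects the blank version.
- Total: 12 − 1 = 11 of 12 items present.
- Limb: 6 − 1 = 5 of 6 items present.
- Fine motor: 3 − 1 = 2 of 3 items present.

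None of these sums can be formed as defined. No visible passage gives an item-level rule for the ALSFRS-R, 8.2 does not impute by default, and the MMRM imputes nothing. In CAFS, a missing ALSFRS-R at the analysis week would be multiply imputed, so CAFS could be computed, but from imputed values in place of observed ones.

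**Case 2: both versions are filled in.** The wrong version can differ from the right one by at most 4 − 0 = 4 points, so one visit's total is wrong by at most 4. That is 4/12, one third of the event threshold. A change from baseline uses two totals, so its arithmetic ceiling is 4 + 4 = 8 points. That is reached only if both visits carry the largest possible error in opposite directions.

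**Case 3: the program takes whichever version was answered.** The effect is 0.

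The documents show neither the case report form nor the derivation program, so they do not say which case applies or how many subjects it would touch.

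**The case against.** The strongest reply is that this is an editorial slip with no likely consequence. In Case 1 a literal program would fail for subjects with and without gastrostomy alike, because each group would be sent to the version it did not answer. Missing totals on that scale would be seen at the first run. A silent error would need both versions to be completed, which nothing in the documents suggests, or a program that ignores the blank and sums 11 items, which departs from the stated definition. This argument stands as to likelihood. It does not make the sentence right.

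Three stronger readings are tempting and are not supported:
- A reader might infer that 8.3.2.1 and Table 4 cannot both be carried out. They can. Table 4 depends on which version was answered, and 8.3.2.1 on which version enters the sum. They conflict in how they label the versions, but King's staging would run correctly whatever the sum does.
- A reader might infer that CAFS cannot be computed because efficacy data are not imputed. The multiple imputation in 8.3.2.2 and 9.2.2.1.1 is exactly the exception that 8.2 allows for.
- A reader might infer that the primary endpoint is biased. No direction or size can be derived without the form and the program.

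The footnote to the total-score bullet needs similar care. It sends the reader to Appendix I of the protocol without saying which protocol, and SAP section 2 lists both the A02 and the A04 protocol as sources. In the A04 protocol Appendix 1 is the El Escorial criteria and the ALSFRS-R is Appendix 2. The reference looks wrong for A04 but cannot be called wrong outright, because the A02 appendices are not available here.

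**Conclusion.** The item 5 rule in SAP 8.3.2.1 is wrong as written. It contradicts Protocol Appendix 2, is at odds with the labelling in the SAP's own Table 4, and is not declared as a change. It is probably a drafting slip and is a minor point. It still deserves correction because it is the stated derivation for the primary-endpoint score in the document that governs the analysis.

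The possible effect depends on facts not shown: nil if the program uses the version answered; totals, limb and fine-motor scores that cannot be formed if it selects a blank version; at most 4 points on one visit's total if both versions were completed. No claim of bias in any result is made.

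**What to change.** Replace the sentence with a rule of this kind: item 5 is the version answered at that visit, 5a for subjects without gastrostomy and 5b for subjects with gastrostomy. At minimum, swap the order to without or with. The version answered is the more workable selector. The schedule of activities lists no assessment of gastrostomy status, and the PEG/RIG switch date in SAP 8.3.1.4 records the route of dosing.

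Confirm that the derivation program follows the rule, and list any visit at which both versions or neither are filled in so that it can be resolved. Do this before the interim database lock, which is the operative one because SAP 5.2 says that the final analysis will not be conducted.

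Check the footnote: name the protocol it refers to and, if that is A04, cite Appendix 2. Table 4 needs no change.

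The cost is one sentence, one footnote reference and one program check. No new data are needed.

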17.4.5.4 Efficacy Analyses for Secondary Endpoints

CAFS analysis ranks clinical outcomes on the basis of survival time and change in the ALSFRS-R score will be analyzed at all visits from baseline in Study MT-1186-A02 to the end of Study MT-1186-A04. In this analysis, a subject's score will be calculated by comparing each subject to every other subject within each treatment group in the study, resulting in a score of +1 if the outcome was better than the subject being compared, -1 if worse, and 0 if the same. The subject's score will then be calculated by summing up their comparison to all of the other subjects within each treatment group in the study as CAFS score. A subject who dies earlier than the comparator subject will be given a comparison score of -1. For a subject who discontinues early for a reason other than death, that subject and the comparator's score will be based on the change from baseline of the ALSFRS-R score at the latest timepoint at which they both have an ALSFRS-R score. In general, these comparisons will result in subjects who die being assigned the worst scores and ranked according to the time of death. Subjects who survive and complete the study will be ranked more favorably than subjects who die. The CAFS score will be evaluated at all visits from

baseline in Study MT-1186-A02 to the end of Study MT-1186-A04 using an ANCOVA model with treatment group and Study MT-1186-A02 randomization strata as fixed effects, and baseline ALSFRS-R total score as covariate. The difference between the 2 treatment groups in the CAFS scores will be also compared using the generalized Gehan-Wilcoxon test as a sensitivity analysis.

The following sequence of parametric and semi-parametric models will be conducted to estimate the clinical benefit:

- Mixed-effect model for repeated measure (MMRM) as specified below.
- COX PH model as specified above.

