3.3. Study Endpoints

3.3.1. Primary Endpoint

The primary efficacy endpoint is time from the randomization date in Study MT-1186-A02 to at least a 12-point decrease in ALSFRS-R or death, whichever happens first.

3.3.2. Secondary Efficacy Endpoints:

The following efficacy endpoints are defined as secondary:

- The Combined Assessment of Function and Survival (CAFS) score at all post baseline visits from MT-1186-A02 until the end of Study MT-1186-A04
- Change in the Amyotrophic Lateral Sclerosis Assessment Questionnaire 40 (ALSAQ-40) score from baseline in Study MT-1186-A02 to all post baseline visits from MT-1186-A02 until the end of Study MT-1186-A04
- Change in ALSFRS-R score from baseline in Study MT-1186-A02 to all post baseline visits from MT-1186-A02 until the end of Study MT-1186-A04
- Time from the randomization date in Study MT-1186-A02 to death, tracheostomy, or permanent assisted mechanical ventilation (≥23 hours/day)
- Time from the randomization date in Study MT-1186-A02 to death or permanent assisted mechanical ventilation (≥23 hours/day)
- Time from the randomization date in Study MT-1186-A02 to death

Mitsubishi Tanabe Pharma America, Inc.

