4.2. Sample Size and Power Considerations

In total, approximately 300 subjects who have successfully completed Study MT-1186-A02 are anticipated to be enrolled in this MT-1186-A04 study. A formal sample size calculation was not performed. However, data from 380 subjects (190 subjects per group) randomized in Study MT-1186-A02 will be included for all analyses. Hence, using MT-1186-A02 and MT-1186-A04 survival data and assuming 65% survival rate of the primary endpoint for the control group, the planned sample size of 190 subjects per group initially randomized in Study MT-1186-A02 will provide 70% power to detect a statistically significant result if the true hazard ratio between edaravone 105 mg daily (test) and edaravone 105 mg on/off regimen (control) in the primary endpoint is HR=0.775 (implying 22.5% risk reduction in the hazard due to daily treatment). This calculation of 70% power assumes a 2-sided alpha of 20% based on a rare disease condition (Hilgers RD et al., 201614) using the log-rank test and a follow-up time of up to 48 weeks in Study MT-1186-A04.

When this SAP version 1.0 was finalized and signed, for 384 subjects randomized in Study MT-1186-A02, 202 subjects who have successfully completed Study MT-1186-A02 were enrolled in this MT-1186-A04 study.

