9.2.2.1.1. Combined Assessment of Function and Survival Score (CAFS)

Multiple imputation analysis assuming MAR

The CAFS will be analyzed using missing imputation under MAR and ANCOVA. This endpoint will be analyzed using the FAS at weeks 24, 48, 72 and 96 (denoted below as week X).

Mitsubishi Tanabe Pharma America, Inc.

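### SAP 8.3.2.2 fixes CAFS scoring at Week 48 and does not say which deaths count at each week, in conflict with the planned analyses at Weeks 24, 48, 72 and 96

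*SAP*

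**What the plan says.** SAP 8.3.2.2 opens by basing CAFS on survival time and the "change in the ALSFRS-R score from baseline in Study MT-1186-A02 to all post baseline visits from MT-1186-A02 until the end of Study MT-1186-A04". SAP 3.3.2 lists the endpoint in the same terms: "The Combined Assessment of Function and Survival (CAFS) score at all post baseline visits from MT-1186-A02 until the end of Study MT-1186-A04". SAP 9.2.2.1.1 sets the analysis weeks: "This endpoint will be analyzed using the FAS at weeks 24, 48, 72 and 96 (denoted below as week X". The reporting-visit table in SAP 10.3 marks the same four weeks.

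The pairwise rule in 8.3.2.2 is narrower:

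- Deaths: "If both participants die, the one surviving longer fared better; if only one survives then that patient fared better".
- Survivors: "if both participants survive, the one with the smaller decline in ALSFRS-R from baseline to week 48 fared better".
- Early discontinuation or a missing Week 48 score: "the participant will be treated as alive at week 48 and the ALSFRS-R at week 48 will be imputed missing using multiple imputation", assuming missing at random.

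The readable scoring and ranking text names no other week. SAP 8.2 points to section 8.3 for the missing-data handling of each variable. Protocol 17.4.5.4 fixes no Week 48. For early discontinuers it makes the comparison "based on the change from baseline of the ALSFRS-R score at the latest timepoint at which they both have an ALSFRS-R score". SAP section 2, however, says that the SAP's statistical details override the protocol's.

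**The concern.** A rule tied to one week cannot yield four visit-specific scores. Read literally, survivors at Weeks 72 and 96 are compared on function at the end of the parent study (A02), and survivors at Week 24 on function measured 24 weeks later. The death comparison has no time limit either. SAP 5.1 says that the analysis takes all data accumulated until A02 stopped, so a death in the extension (A04) would place that subject below every survivor in the Week 24 score as well.

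The label is also ambiguous. SAP Table 5 equates A04 Week 48 with Week 96, and SAP 4.1 uses plain Week 48 for the A04 end-of-treatment visit. If that is what 8.3.2.2 means, the Week 24, 48 and 72 scores are the misaligned ones.

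At stake is the only secondary endpoint that combines function and death. It is also at stake whether ALSFRS-R collected in A04 enters the functional ranking at all.

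**Working it through.** **Plan's own figure.** The documents give no power or effect figure for CAFS. Their one power figure, 70%, concerns the primary endpoint. It reproduces with exponential survival and no dropout:

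- Control event-free at Week 96: 0.65² = 0.4225. Daily arm: 0.4225^0.775 = 0.5129.
- Expected events: 190 × 0.5775 + 190 × 0.4871 = 202.3.
- Schoenfeld power at 2-sided alpha 20%: 70.2%.

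Nothing below changes that figure.

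**Sections side by side.**

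| Element | Week given in 8.3.2.2 | Week needed by 3.3.2, 9.2.2.1.1 and 10.3 |
|---|---|---|
| Survivor change in ALSFRS-R | 48 | 24, 48, 72, 96 |
| Alive status after early discontinuation or missing score | 48 | 24, 48, 72, 96 |
| Imputed score | 48 | 24, 48, 72, 96 |
| Deaths that count | not stated | deaths up to each analysis week |

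**Consequence of the literal rule.** A subject's score is the sum, over all other subjects, of +1, 0 or −1. Each comparison depends only on the two death dates and the two changes to Week 48. The analysis week is not an argument of the rule, so for a single data cut the score at Weeks 24, 48, 72 and 96 is the same number.

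**Invented four-subject example** (change from baseline; C dies on Day 600):

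| Subject | Wk 24 | Wk 48 | Wk 72 | Wk 96 |
|---|---|---|---|---|
| A | −2 | −12 | −16 | −20 |
| B | −5 | −8 | −18 | −24 |
| C | −1 | −3 | −6 | dead |
| D | −9 | −14 | −19 | −22 |

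Scores:

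| Rule | A | B | C | D |
|---|---|---|---|---|
| As printed, all four weeks | +1 | +3 | −3 | −1 |
| Week X = 24 | +1 | −1 | +3 | −3 |
| Week X = 48 | −1 | +1 | +3 | −3 |
| Week X = 72 | +1 | −1 | +3 | −3 |
| Week X = 96 | +3 | −1 | −3 | +1 |

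The week-X rows use change to week X and only deaths up to week X. They are the same whether the death cut-off is the nominal day (169, 337, 505, 673) or the window end (211, 379, 546, 715), because Day 600 lies after 546 and before 673. Under the printed rule C has the worst score at Weeks 24, 48 and 72 while alive with the smallest decline. Week 48 itself is therefore affected, through the missing death cut-off.

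**Imputation.** SAP 4.2 reports that "for 384 subjects randomized in Study MT-1186-A02, 202 subjects who have successfully completed Study MT-1186-A02 were enrolled in this MT-1186-A04 study". So 384 − 202 = 182 randomized subjects (182/384 = 47.4%) had not been enrolled in A04 at SAP signing. On that count, each of them who is not dead by Week 72 or 96 needs an imputed score there, and the visible text gives an imputation rule for Week 48 only.

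**The case against.** The best defence is that the plan clearly intends a score for each visit. The opening sentence of 8.3.2.2, SAP 3.3.2, 9.2.2.1.1 and 10.3 all say so. Section 9.2.2.1.1 announces week X notation for text that is not in the available copy, and Figures 2 and 3 (the scoring and ranking examples) are not shown either. That material may hold the right derivation and cannot be counted as missing from the plan. Carried-over wording is a plausible cause: SAP 8.3.2.1 likewise describes domain scores as change to Week 48, while 9.2.2.1.2 analyses each domain at all visits to Week 96. The phrase about being alive at Week 48 also suggests that vital status is judged at the analysis week.

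Most of this stands as evidence of intent. It does not remove the conflict. The fixed week is in legible text, in the section to which SAP 8.2 assigns missing-data handling. If 9.2.2.1.1 does use week X, two SAP sections disagree. The alive-status phrase covers only subjects who discontinue early or lack a Week 48 score. It does not cover a subject who has that score and dies later. The protocol's latest-shared-timepoint rule cannot fill the gap, because the SAP overrides it.

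A reader might go further and infer that the Week 24, 72 and 96 scores will in fact fail to measure outcome at those weeks. The documents do not support that as a fact. It follows only if 8.3.2.2 is programmed word for word.

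**Conclusion.** The inconsistency is real and worth correcting. As written, 8.3.2.2 fixes survivor change, alive status and imputation at Week 48 and leaves the countable deaths at each week unstated, against four other statements in the same SAP. Identical scores at all four weeks follow if the rule is applied literally to one data cut. The programmed analysis may differ.

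The reach is limited. SAP 9.2.2 analyses secondary endpoints with nominal p-values and no prespecified order. The primary endpoint does not use CAFS.

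A reader might also infer a definite loss of power. The documents do not allow one to be calculated. It would depend on decline rates, death rates and the timing of any effect, none of which they give for CAFS, and on how much Week 96 function was observed. Only 202 of 384 had entered A04 at SAP signing, both studies were being stopped, and SAP 5.2 cancels the final analysis, so much of the late function would be imputed under either rule. An effect that arose only after Week 48 would vanish from a Week 48 functional ranking by construction, which says nothing about its size here.

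**What to change.** In SAP 8.3.2.2:

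1. Replace each Week 48 with week X, where X = 24, 48, 72 or 96 counted from A02 Day 1, for survivor change, vital status and imputation.
2. State that only deaths up to the end of the Week X analysis window in Table 5 count as deaths (Day 211, 379, 546, 715), and that later deaths are treated as alive at week X.
3. Reconcile the section with the week X text of 9.2.2.1.1.

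The window end is preferable to the nominal day. SAP 8.3.2.3 ties King's Stage 5 to the last day of the analysis visit window, and the Week 48 window runs from Day 295 to 379. With a nominal-day cut-off (Day 337), a subject who died on Day 340 without a Week 48 assessment would be alive with imputed function for CAFS, while King's staging could record Stage 5.

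The cost is a wording change in one SAP section and a week parameter in one program. No new data are needed. If the analysis has already been run, the rule actually used at each week should be stated in the study report, where SAP section 2 places deviations from the plan.
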